#### Maternal utilization of mental health services

Analyses of outcomes related to maternal utilization of mental health services is also planned as a stand-alone analysis. NFP guidelines require nurses to screen for depression and anxiety at pre-specified intervals throughout the program, and to follow their agencies' protocols for referral and care coordination for women who screen positive. While directly measuring the

prevalence of depression and anxiety in our study sample would help us assess the impact of NFP on mental health, our study design relies exclusively on administrative data sources for outcome measurement. Therefore, our study design will seek to analyze how NFP changed the utilization of mental health services during the perinatal period.

We include all women with an index birth in our analytic sample, regardless of whether they had a prior mental health diagnosis before pregnancy. Because few women in our study are enrolled in Medicaid prior to pregnancy, we cannot observe prior diagnoses or identify treatment initiation. However, we expect rates of prior mental health diagnoses before pregnancy to be equal across treatment and control arms. Because the outpatient mental health treatment outcomes rely exclusively on Medicaid claims, we will restrict the analytic sample for outpatient outcomes to those women who retain full Medicaid coverage through 60 days postpartum. We will not restrict the sample for inpatient mental health outcomes as these rely on utilization that will be observable in all-payer hospital discharge data, regardless of payer.

While the medical definitions for depression and anxiety are distinct, we examine them together because they are comorbid conditions and NFP screens for them simultaneously. We define outpatient mental health treatment as a composite outcome of either a diagnosis for depression/anxiety/stress reaction or a filled prescription for antidepressants/anxiolytics or an outpatient psychotherapy visit during pregnancy or the first 60 days postpartum. We list the ICD-10 diagnosis codes, therapeutic class codes, and Current Procedure Terminology (CPT) codes used to define these outcomes in Tables 1.4, 1.5, and 1.6. Consistent with prior research, we consider all outpatient psychotherapy visits, including individual, family or group therapy to be mental health visits.

Table 1.4. Diagnosis codes for depression/anxiety/stress reaction

Code description	ICD-10 Code(s)

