Depression	F53; O906; F99; O9934*; F32*; F33*
Anxiety	F41.*
Stress-reaction	F43.*

Table 1.5. Therapeutic class codes for filled antidepressants or anxiolytics

Code description	Therapeutic class codes
Antidepressants	281604

Anxiolytics	2824*
-------------	-------

Table 1.6. Outpatient psychotherapy codes

Code description	CPT codes
Psychotherapy (individual, family or group)	90804-90815; 90832-90834; 90836- 90840; 90845-90847; 90849; 90853; 90857; 90862; 90875; 90876

We will also look at these outpatient measures individually (i.e., diagnosis, filled prescription, and psychotherapy) and in combination to enhance our understanding of treatment patterns. For example, we may be interested in the proportion of mothers who receive a diagnosis but do not fill a prescription or receive psychotherapy as this could signal structural or individual-level barriers to treatment. We may also be interested in the proportion of women who receive medication only, as psychotherapy is often recommended as a first-line treatment for mild or moderate depression and in combination with medication when the depression is severe. We may also explore the timing of outpatient mental services (measured in days). NFP could lead to earlier treatment of perinatal depression/anxiety through regular screening, coordinating care, providing a warm hand-off, or by reducing the stigma surrounding mental health and treatment.

For most of the outcomes related to outpatient mental health treatment, we restrict the measurement period to pregnancy through 60 days postpartum because these outcomes are derived from Medicaid claims data and maintenance of coverage past 60 days may be affected by participation in NFP. However, depression and anxiety can take longer than 60 days to manifest, and even longer for the mother to access healthcare. In future analyses, we will consider measuring outpatient mental health treatment patterns through 6, 12 and 24 months postpartum if treatment and control group members are equally likely to be enrolled in *full-coverage* Medicaid plans through these time points.

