For inpatient mental health outcomes, we will use hospital discharge data to measure mental health related visits on both the extensive and intensive margins. Specifically, we will create an indicator for any mental health related emergency or inpatient visits during pregnancy or the 12 months postpartum based on all-listed diagnoses (i.e. primary or secondary) for depression/anxiety/stress reaction, excluding inpatient claims on the day of delivery. We will also create a count variable for the number of mental health related emergency or inpatient visits during pregnancy or the 12 months postpartum based on all-listed diagnoses for depression/anxiety/stress reaction, excluding inpatient claims on the day of delivery. We examine these hospital-related outcomes because public insurance pays for six of every ten inpatient stays related to mental health, and they could indicate inadequate outpatient treatment for perinatal depression and anxiety. We may also look at diagnoses for depression/anxiety/stress on the day of delivery, as prior research has found that a large proportion of women have diagnoses on this day. These diagnoses may represent cases where women had subclinical or previously unidentified symptoms during pregnancy that were identified during the hospital stay. Finally, we may construct an outcome that captures the proportion of women who have an emergency or inpatient stay related to mental health without any medication or outpatient psychotherapy treatment during pregnancy or the 12 months postpartum.

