**Table 8. Mental health outcomes**

	Primary/secondary	Desired direction (increase or decrease)

Any outpatient treatment or diagnosis (preg-60d)	secondary	increase
Antidepressant prescription (preg-60d)	secondary	increase
Outpatient mental health visit (preg-60d)	secondary	increase
Treatment follow up (within 120d)	secondary	increase
Mental health related emergency/inpatient visit (preg-1y)	secondary	decrease
Number of mental health related emergency/inpatient visits (preg-1y)	secondary	decrease
Neonatal abstinence disorder or maternal drug/substance use (2y)	secondary	decrease
Maternal experience of violence or homicide (2y)	secondary	decrease

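### Counting depression, anxiety or stress codes in any diagnosis position could bias the mental-health emergency/inpatient outcomes upward in the NFP arm, and no principal-diagnosis version is planned to check this

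*SAP*

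**What the plan says.** SAP Addendum 1, Maternal utilization of mental health services, builds an any-visit indicator from hospital discharge data for pregnancy and the 12 months after birth, "based on all-listed diagnoses (i.e. primary or secondary) for depression/anxiety/stress reaction, excluding inpatient claims on the day of delivery". The count follows the same rule: "We will also create a count variable for the number of mental health related emergency or inpatient visits during pregnancy or the 12 months postpartum". One reason given for studying these visits is that "they could indicate inadequate outpatient treatment for perinatal depression and anxiety".

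The same section describes what NFP does in this area: "NFP guidelines require nurses to screen for depression and anxiety at pre-specified intervals throughout the program", with referral under agency protocols for women who screen positive. It adds: "NFP could lead to earlier treatment of perinatal depression/anxiety through regular screening, coordinating care, providing a warm hand-off".

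On hospital coding, the section comments only on diagnoses made on the delivery day: "These diagnoses may represent cases where women had subclinical or previously unidentified symptoms during pregnancy that were identified during the hospital stay".

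In SAP Addendum 4, Table 8, the first row (any outpatient treatment or diagnosis, pregnancy to 60 days) has the desired direction increase. The fifth and sixth rows (the emergency/inpatient indicator and count, pregnancy to one year) have decrease. The Outcomes section of Addendum 4 combines such rows into indices. It also accepts that NFP could move emergency department use either way and puts those outcomes in Table 11, mostly without a direction. The mental-health emergency outcomes stay in Table 8.

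**The concern.** An all-listed rule mixes two kinds of record: visits made because of a mental health problem, and visits for something else on which a known diagnosis is also listed. The second kind depends on how many women have a recorded diagnosis. The plan expects NFP to act on detection and treatment, so that number may differ by arm even if hospital use does not.

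If so, better detection in the NFP arm would raise an outcome that is meant to fall. A null or adverse result could not be told apart from more complete coding, and a true fall in crisis visits could be hidden. In the Table 8 index, two of the eight rows would pull against the wanted rise in outpatient diagnosis and treatment.

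The planned checks do not address this. The attrition analyses in the section concern Medicaid coverage. The all-payer source removes dependence on payer, not on coding.

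**Working it through.** The documents give no rate, effect size or power for these outcomes, so there is no planned figure to reproduce. The check asks how large a purely coding-driven gap could be.

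**Inputs from the documents**
- Women with an index birth: 3295 NFP, 1637 control (SAP Addendum 4, Table 3). Addendum 1 includes all women with an index birth and does not restrict the sample for inpatient outcomes.
- Two-sided significance level 0.05 (Protocol section 5.1).

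**Assumed inputs, not in the documents**
- v, share of women with any non-delivery emergency or inpatient visit: 50 to 70%.
- d, share of controls with a recorded depression/anxiety/stress diagnosis: 15 to 25%.
- c, share of diagnosed women with a visit whose code is listed as secondary: 30 to 60%.
- p, share with a visit for which it is the principal diagnosis: 2%.
- x, ratio of recorded diagnoses, NFP to control: 1.10 or 1.25.
- True hospital use and the listing share c are the same in both arms.

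**Formulas**
- Control rate = p + (1 − p)·v·d·c
- NFP rate = p + (1 − p)·v·d·x·c
- The probability of a significant excess in the NFP arm uses the normal approximation for two proportions, with pooled standard error under the null and unpooled under the alternative. Its nominal value is 2.5%.

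**Smallest and largest cases at x = 1.10**
- v = 0.5, d = 0.15, c = 0.3. Control: 0.02 + 0.98 × 0.0225 = 4.20%. NFP: 0.02 + 0.98 × 0.02475 = 4.43%. Gap 0.22 points.
- v = 0.7, d = 0.25, c = 0.6. Control: 0.02 + 0.98 × 0.105 = 12.29%. NFP: 0.02 + 0.98 × 0.1155 = 13.32%. Gap 1.03 points.

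| Rise in recorded diagnoses | Spurious gap (points) | Rate ratio | Probability of a significant NFP excess |
|---|---|---|---|
| none | 0 | 1.00 | 2.5% |
| 10% | 0.2 to 1.0 | 1.05 to 1.08 | 5 to 17% |
| 25% | 0.6 to 2.6 | 1.13 to 1.21 | 13 to 69% |

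Under the same assumptions a principal-diagnosis version shows no gap, provided that screening does not itself change principal coding.

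**Masking.** Take v = 0.6, d = 0.2, c = 0.45 and a true 20% fall in principal-diagnosis visits.
- p = 2% (true change −0.40 points). Control: 0.02 + 0.98 × 0.054 = 7.29%. NFP at x = 1.10: 0.016 + 0.984 × 0.0594 = 7.44%, an apparent rise of 0.15 points. At x = 1.25 the apparent rise is 0.95 points.
- p = 4% (true change −0.80 points). At x = 1.10 the all-listed outcome still falls, by 0.23 points. At x = 1.25 it rises by 0.55 points.

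The net direction therefore depends on inputs that the documents do not supply.

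**The case against.** A reader might infer that the error is shown to differ by arm and to make NFP look harmful. The documents do not support that. They make it plausible that NFP raises recorded diagnoses, but say nothing about whether those diagnoses carry over to unrelated hospital records. Hospitals may also find unrecognised symptoms themselves. The SAP says this of the delivery day; if it happens at other visits, controls gain codes too. Better outpatient care could also prevent more visits than coding adds.

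A large single figure is also tempting. With 20% against 15% diagnosed, two unrelated visits for every woman and a 30% chance of listing at each, the rates are 0.20 × 0.51 = 10.2% and 0.15 × 0.51 = 7.65%, a gap of about 2.6 points. That fixes a 33% relative rise in diagnosis. With a 10% rise and visits in only 60% of women, the same formula gives 5.05% against 4.59%, about 0.5 points.

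Nor does Table 8 simply score one event as both benefit and harm. Its first row is a composite of diagnosis, filled prescription or psychotherapy, from Medicaid claims to 60 days. The hospital outcomes are all-payer and run to one year.

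The all-listed rule is an openly stated choice that suits a domain framed as service use, and the SAP says only that these visits could indicate inadequate treatment. First-listed coding has its own loss: a crisis visit whose first code lies outside SAP Table 1.4 would be missed. This stands, and it argues against replacing the main definition.

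The SAP also mentions a possible outcome for mental-health stays without medication or outpatient psychotherapy. It is closer to inadequate treatment, but it is optional and sets no separate diagnosis-position rule.

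On delivery, a stay spanning the delivery date can reasonably be read as already excluded, and later billing within a stay fits discharge records poorly. What remains is that the SAP does not say which date governs. If it is the admission date, a stay begun the day before delivery can count. No difference between arms follows from this alone.

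**Conclusion.** The concern holds as a risk of bias that the plan leaves unchecked. The all-listed outcomes could be biased upward in the NFP arm, and the plan has no version that would show it. The gap of 0.2 to 1.0 points at a 10% rise in recorded diagnoses, and 0.6 to 2.6 points at 25%, rests wholly on the assumed visit, diagnosis and listing rates and on no true difference. It illustrates scale and does not predict the result.

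The reach is limited. These are secondary outcomes in a stand-alone analysis, and the primary endpoints are unaffected. The decrease label is explicit only in Addendum 4; Addendum 1 implies it. The effect on the Table 8 index has not been quantified. The point still deserves action because it changes what a null or adverse result on these outcomes can mean.

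**What to change.** - Keep the all-listed definition. Pre-specify a principal (first-listed) diagnosis version of both the indicator and the count, reported beside it. Addendum 4 describes the trial's manuscripts as published or forthcoming, so label this version as added later if mental-health results already exist.
- Re-run the Table 8 index with the principal-diagnosis version as a sensitivity analysis. Addendum 4 states that its own analyses had not been performed when it was submitted.
- State that an increase on the all-listed outcomes will not be read as harm unless the principal-diagnosis version agrees.
- Exclude the whole delivery hospitalisation, meaning any stay whose admission-to-discharge dates span the delivery date.

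The cost is SAP wording, a diagnosis-position filter on discharge data that the plan already uses, and a little more analysis. The principal-diagnosis version will have fewer events and miss some true cases, which the retained all-listed version covers.

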In our clinical trials registry, we defined a measure of mental health treatment follow-up care as: a second antidepressant prescription or outpatient mental health visit within 120 days of the initial treatment ("acute phase"). However, as noted above, differential Medicaid coverage rates between the treatment arms after 60 days postpartum may preclude us from measuring the treatment effect for this outcome reliably. For example, if treatment group members are more likely to be enrolled in Medicaid after 60 days postpartum than control group members, observed differences in mental health treatment patterns between the treatment and control groups could be due to group differences in the composition of who remains on Medicaid.

To assess whether attrition from full-coverage Medicaid plans affects the comparability of the treatment and control groups, we will assess overall attrition and differences in attrition between the treatment and control groups at the following time points: 60 days (for our main outpatient mental health treatment outcomes), 6 months, 12 months and 24 months postpartum (for other potential measurement periods of interest). We do not consider enrollment in partial-coverage Medicaid plans (such as Family Planning) since these plans cover mental health screenings, but do not reimburse for medications or psychotherapy. Specifically, we will compare partial and continuous enrollment rates in full coverage plans between treatment and control groups at each time point. Continuous coverage will be measured using Medicaid enrollment data and will be defined as enrollment during all months, starting with the month of childbirth through 60 days, 6 months, 12 months and 24 months postpartum. It's possible that while average Medicaid enrollment will not differ between the two groups, the type of women retaining coverage could be affected by NFP. Therefore, we will also test whether the treatment and control group members who remain in the analytic sample at each time point are similar on important baseline characteristics using a joint F-test.

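### The optional 12-month outcome of a mental health hospital visit without treatment can see treatment only in Medicaid claims, so care given entirely outside full Medicaid coverage is counted as no care

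*SAP*

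**What the plan says.** All of this is in SAP Addendum 1, under Maternal utilization of mental health services, unless noted.

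- **The outcome.** It is optional: "Finally, we may construct an outcome that captures the proportion of women" is followed by the definition, an "emergency or inpatient stay related to mental health without any medication or outpatient psychotherapy treatment during pregnancy or the 12 months postpartum". It closes the paragraph on inpatient outcomes.
- **Hospital half.** "For inpatient mental health outcomes, we will use hospital discharge data to measure mental health related visits". On the sample: "We will not restrict the sample for inpatient mental health outcomes", because these visits can be seen whoever pays.
- **Treatment half.** The sample rule for outpatient outcomes opens: "Because the outpatient mental health treatment outcomes rely exclusively on Medicaid claims". The plan therefore decides to "restrict the analytic sample for outpatient outcomes to those women who retain full Medicaid coverage through 60 days postpartum".
- **Window.** For most outpatient measures the window ends at 60 days, because "maintenance of coverage past 60 days may be affected by participation in NFP". Windows of 6, 12 and 24 months are left to future analyses, on condition that the arms are equally likely to hold full coverage.
- **Coverage checks.** Full-coverage enrolment is to be compared by arm at 60 days and at 6, 12 and 24 months, with a joint F-test on baseline characteristics. Partial plans such as Family Planning do not count, since "these plans cover mental health screenings, but do not reimburse for medications or psychotherapy".

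**The concern.** The reason given for leaving the inpatient sample unrestricted is that discharge data cover every payer. That is true of the hospital visit. It is not true of the second half of this outcome, which needs 12 months of prescription and psychotherapy records and has only Medicaid claims to supply them.

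In most claims outcomes a missing claim loses an event. Here a missing claim creates one, because the event is defined by the absence of treatment. The woman affected has a mental health visit and is treated, but only while she lacks full Medicaid coverage, for example after coverage ends past day 60, under another payer or at her own expense.

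Two consequences follow. The recorded proportion is too high in both arms. If home visiting helps women keep full coverage, fewer programme mothers are wrongly counted as untreated, and the outcome shows a benefit even when care is identical. The plan uses this same reasoning to shorten most outpatient measures, but attaches neither the 60-day rule nor the coverage checks to this one.

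**Working it through.** The documents state no rate, power or sample size for this outcome, so there is no figure to reproduce.

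**Is loss of coverage plausible?** SAP section 3.5 says pregnancy coverage lasts at least 60 days after childbirth, with exceptions for some immigrants. SAP Table 2 gives income limits of 199% of the poverty line for pregnant women and 67% for parents from January 2016 to January 2020 (194% and 95% in January 2021). Substantial loss after day 60 is therefore plausible, but its size is not given.

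**Inputs.** From the documents: 3,295 home visiting and 1,637 usual care mothers with an index birth (Addendum 4, Table 3), and a two-sided 0.05 test (protocol section 5.1). Assumed:
- v = 5% have a mental health hospital visit.
- t = 50% of these are truly treated, in both arms.
- L = 30% or 50% of the treated have all their treatment after day 60.
- c = share with full coverage after day 60: 40% in control, 50% or 60% under NFP.
- Women without full coverage are treated as often as the others, through sources that Medicaid claims do not show.

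**Formulas.** True rate = v(1 − t) = 0.05 × 0.5 = 2.5%. Recorded rate = v[(1 − t) + t·L·(1 − c)]. False arm difference = v·t·L × (control c − NFP c).

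| L | Control, c = 40% | NFP, c = 50% | NFP, c = 60% |
|---|---|---|---|
| 30% | 0.05 × 0.590 = 2.95% | 0.05 × 0.575 = 2.875% | 0.05 × 0.560 = 2.80% |
| 50% | 0.05 × 0.650 = 3.25% | 0.05 × 0.625 = 3.125% | 0.05 × 0.600 = 3.00% |

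- **Level.** Control is overstated by 0.45/2.5 = 18% to 0.75/2.5 = 30%.
- **False difference.** For L = 30%: −0.075 points (−2.5% relative) and −0.15 points (−5.1%). For L = 50%: −0.125 points (−3.8%) and −0.25 points (−7.7%).
- **Against sampling error.** The smallest case has SE = √(0.0295 × 0.9705/1,637 + 0.02875 × 0.97125/3,295) = 0.51 points, and 0.075/0.51 = 0.15. The largest has SE = √(0.0325 × 0.9675/1,637 + 0.03 × 0.97/3,295) = 0.53 points, and 0.25/0.53 = 0.47. The chance of a significant result with no true effect is then about 5% to 8%.

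**Wider range.** With v from 5% to 15%, t from 50% to 70%, L from 10% to 50% and 40% coverage in control, 6% to 41% of control events are false. Type I error is 5.1% to 10.5% for a 10-point coverage gap and 5.2% to 28.1% for a 20-point gap. The 28.1% needs v = 15%, t = 70% and L = 50% together.

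**Equal coverage in both arms.** The false difference vanishes, but a real one is multiplied by 1 − L(1 − c). With v = 10%, treated shares of 50% and 60%, and c = 40%, a true −1.0 point becomes −0.94 (L = 10%) to −0.70 (L = 50%). Power falls from 37% to between 32% and 17%.

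**The case against.** **The plan already has the tools.** It compares full coverage by arm at 12 months and permits longer outpatient windows only under balance. One can argue that the treatment half is itself an outpatient outcome and so already falls under those rules. This stands in part: the checks would expose differential coverage. But the plan files the measure among the inpatient outcomes, which it leaves unrestricted, and no cross-reference ties the checks to it. Balance would also leave the inflated level and the dilution.

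**Few women are misclassified.** This stands. A reader might infer that losing coverage after day 60 by itself turns a treated woman into an untreated one. It does not, because the definition asks for any treatment over the whole window, so one claim in pregnancy, the first 60 days or a later covered month is enough. The factor L carries this.

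**Some of the effect may be real.** This stands too. A woman who loses coverage and truly goes without care is correctly counted. If retention of coverage improves treatment, part of the arm difference is a true programme effect, whereas the illustration assumes equal care.

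**Another source might fill the gap.** The data use agreements listed in protocol section 4.7.1 include matched Department of Mental Health diagnoses and services. The SAP does not name these data for this outcome.

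**Further readings the text does not support.** A reader might infer that every other outpatient measure stops at 60 days. The plan says most, and Addendum 4 Table 8 lists a 120-day follow-up measure. A reader might also apply to this outcome the plan's remark that hospital use could point to inadequate outpatient care. That remark concerns the visit indicator and the visit count. Nor is this outcome labelled secondary anywhere.

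**Conclusion.** The concern holds as a flaw in the definition of one optional outcome. Followed as written, the plan counts a woman with a hospital visit as untreated when all her treatment lies outside what Medicaid claims can show.

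That false events arise follows from the plan's own statements about its data sources, provided some women are treated outside Medicaid. Their number rests wholly on assumed rates. In the main illustration the level is overstated by 18% to 30%, while the false arm difference is at most 0.25 points, under half a standard error. The direction favours the programme only if the programme improves retention of full coverage, which the plan treats as possible and not as known. Larger distortions of the test need several unfavourable assumptions at once.

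A reader might infer that the trial's mental health findings in general are compromised. The documents do not support that: the outcome is absent from Addendum 4 Table 8, and no primary or listed outcome depends on it. This is a cheap improvement of low severity.

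**What to change.** Amend the paragraph on inpatient mental health outcomes in SAP Addendum 1:

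1. State the data source for the medication and psychotherapy component.
2. Define the version used to compare arms over pregnancy to 60 days postpartum, for both the hospital visit and the absence of treatment, in women with full Medicaid coverage through 60 days. This is the rule already set for the main outpatient outcomes.
3. Report the 12-month version only descriptively, by months of full coverage and arm. Alternatively, compare arms on it only if the planned coverage comparison and joint F-test show balance at 12 months, with a sensitivity analysis in continuously covered women. That analysis reopens the question of who keeps coverage, so it should support the comparison and not replace it.

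The cost is a paragraph of wording. The comparative version will have fewer events and will miss the late-onset cases that the plan itself considers important, which is the reason to keep a 12-month description beside it.
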